- The investigator will use clinical judgment to determine the relationship.
- Alternative causes, such as underlying disease(s), concomitant therapy, and other risk factors, as well as the temporal relationship of the event to study treatment administration will be considered and investigated.
- The investigator will also consult the Investigator's Brochure and/or Product Information, for marketed products, in his/her assessment.
- For each adverse event/serious adverse event, the investigator must document in the medical notes that they have reviewed the adverse event/serious adverse event and has provided an assessment of causality. For sites reporting serious adverse events via electronic data capture (EDC), the investigator or sub-investigator must confirm causality in EDC within 72 hours of the serious adverse event being entered on the Events CRF.
- There may be situations in which a serious adverse event has occurred and the investigator has minimal information to include in the initial report. However, it is very important that the investigator always make an assessment of causality for every event before the initial transmission of the serious adverse event data.
- The investigator may change his/her opinion of causality in light of follow-up information and send a serious adverse event follow-up report with the updated causality assessment. In this case, for sites reporting serious adverse events via EDC, the investigator or sub-investigator must reconfirm causality in the EDC system within 72 hours of the serious adverse event being entered on the Events CRF.
- The causality assessment is 1 of the criteria used when determining regulatory reporting requirements.

Follow-up of Adverse Event and Serious Adverse Event

- The investigator is obligated to perform or arrange for the conduct of supplemental measurements and/or evaluations as medically indicated or as requested by Amgen to elucidate the nature and/or causality of the adverse event or serious adverse event as fully as possible. This may include additional laboratory tests or investigations, histopathological examinations, or consultation with other health care professionals.
- If a subject is permanently withdrawn from investigational product(s) and/or noninvestigational product(s)/auxiliary medicinal product(s) because of a serious adverse event, this information must be submitted to Amgen.

- If a subject dies during participation in the study or during a recognized follow-up period, the investigator will provide Amgen with a copy of any postmortem findings including histopathology.
- New or updated information will be recorded in the originally completed Events CRF.
- The investigator will submit any updated serious adverse event data to Amgen immediately and no later than 24 hours of receipt of the information.

Reporting of Serious Adverse Event

Serious Adverse Event Reporting via Electronic Data Collection Tool

- The primary mechanism for reporting serious adverse event will be the EDC system.
- If the EDC system is unavailable, then the site will report the information to Amgen using a paper-based Serious Adverse Event Contingency Report Form (also referred to as the electronic Serious Adverse Event Contingency Report Form) (see [Figure 11-1](#)) immediately and no later than 24 hours of the investigator's awareness of the event.
- **The primary mechanism for the site to report the Other Safety Finding/Special Situation associated with a serious adverse event to Amgen is by submitting the Clinical Trial electronic serious adverse events Contingency Report Form immediately and no later than 24 hours of the investigator's awareness of the event.**
- The site will enter the serious adverse event data into the electronic system as soon as it becomes available.
- After the study is completed at a given site, the EDC system will be taken off-line to prevent the entry of new data or changes to existing data.
- If a site receives a report of a new serious adverse event from a study subject or receives updated data on a previously reported serious adverse event after the EDC system has been taken off-line, then the site can report this information on the paper-based Serious Adverse Event Contingency Report Form (see [Figure 11-1](#)).
- Once the study has ended, serious adverse event(s) suspected to be related to investigational product will be reported to Amgen immediately and no later than 24 hours of the investigator's awareness of the event. The investigator should use the paper-based Serious Adverse Event Contingency Report Form to report the event.

Figure 11-1. Sample Electronic Serious Adverse Event Contingency Report Form (paper-based form)

Completion Instructions
Clinical Trial Electronic Serious Adverse Event Contingency Report Form (paper-based form)
 (For use for clinical trial studies using Electronic Data Capture [EDC])

NOTE: This form is to be used under restricted conditions outlined on page 1 of the form below. If you must fax or email an event report to Amgen, you must also enter that event into the EDC system (eg, Rave) when it becomes available.

General Instructions
 The protocol will provide instruction on what types of events to report for the study. This form is to be used ONLY to report events that must be captured in the Amgen safety database. *Indicates a mandatory field.

Types of Events to be reported on this form

- Serious Adverse Events (SAE), regardless of causal relationship to Investigational Product (IP)
- Other Safety Findings/Special Situations associated with a Serious Adverse Event (SAE)

1. Site Information
 Site Number* – Enter your assigned site number for this study
 Investigator*, Country*, Reporter*, Phone No., and Fax No. – Enter information requested

2. Subject Information
 Subject ID Number* – Enter the entire number assigned to the subject
 Age at event onset, Sex, and Race – Enter the subject's demographic information
 End of Study date – If the subject has already completed the study or terminated the study early, enter the End of Study date

If you are submitting follow-up information to a previous report, provide the serious adverse event term for the previous report as well as the start date for the initial event.

3. Serious Adverse Event OR Other Safety Finding/Special Situation associated with a Serious Adverse Event
 Provide the date the Investigator became aware of this Information

Other Safety Finding/Special Situation associated with a Serious Adverse Event*

- If the Other Safety Finding (OSF)/Special Situation (SS) (medication error, misuse, abuse) is associated with a serious adverse event, record/report the serious adverse event on the Events Case Report Form in the EDC system and report the associated OSF/SS using this paper-based Serious Adverse Event Contingency Report Form.
- If the OSF/SS (medication error, misuse, abuse) is associated with a serious adverse event, in addition to completing section 3 of this form, please complete all other sections of this form (sections 1 – 10).
- If the EDC system is not available to record/report the serious adverse event on the Events Case Report Form, then report both the OSF/SS and the associated serious adverse event using this form.
- Do not enter Pregnancy or Lactation exposures or Product Complaints on this form. These must be collected/reported per the study protocol.

Serious Adverse Event Diagnosis or Syndrome* or Other Safety Finding/Special Situation with a Serious Adverse Event* –

- If the diagnosis is known, it should be entered. Do not list all signs/symptoms if they are included in the diagnosis.
- If a diagnosis is not known, the relevant signs/symptoms should be entered.
- If the event is fatal, the cause of death should be entered and autopsy results should be submitted, when available.
- The entry of death is not acceptable, as this is an outcome.

Date Started* – Enter date the adverse event first started (not the date on which the event met serious criteria) rather than the date of diagnosis or hospitalization. This is a mandatory field.

Date Ended – Enter date the adverse event ended and not the date when the event no longer met serious criteria. If the event has not ended at the time of the initial report, a follow-up report should be completed when the end date is known. If the event is fatal, enter the date of death as the end date.

If event occurred before the first dose of Investigational Product (IP)/drug under study, add a check mark in the corresponding box.

Is event serious?* – Indicate Yes or No. This is a mandatory field.

Serious Criteria Code* – This is a mandatory field for serious events. Enter all reasons why the reported event has met serious criteria:

- Immediately life-threatening – Use only if the subject was at immediate risk of death from the event as it occurred. Emergency treatment is often required to sustain life in this situation.
- If the investigator decides an event should be reported in an expedited manner, but it does not meet other serious criteria, "Other Medically Important Serious Event" may be the appropriate serious criterion.

Relationship to IP – The Investigator must determine and enter the relationship of the event to the IP at the time the event is initially reported. This is a mandatory field.

FORM-494035, Effective Date: 30 Nov 2023, Version: 3.0

Completion Instructions – Clinical Trial Electronic Serious Adverse Event Contingency Report Form
(for use for clinical trial studies using Electronic Data Capture [EDC])

Note, this form is to be used under restricted conditions outlined on page 1 of the form. If you must fax or email an event report to Amgen, you must also enter that event into the EDC system (eg, Rave) when it becomes available.

Relationship to investigational device (Amgen investigational device and/or a non-Amgen investigational device)* –
The Investigator must determine and enter the relationship of the event to the device (e.g. prefilled syringe, auto-injector) at the time the event is initially reported. If the study involves an Amgen or non-Amgen investigational device, this is a mandatory field.

Please note, this question does not apply to non-Amgen devices used in the study (e.g. heating pads, infusion pumps).

Outcome of Event* – Enter the code for the outcome of the event at the time the form is completed. This is a mandatory field.

- Resolved – End date is known
- Not resolved / Unknown – End date is unknown
- Fatal – Event led to death

If event is related to a study procedure, such as a biopsy, radiotherapy or withdrawal of a current drug treatment during a wash-out period, add a check mark to the corresponding box. This does not include relationship to IP or concomitant medication – only diagnostic tests or activities mandated by the protocol.

4. Hospitalization

If the subject was hospitalized, enter admission and discharge dates. Hospitalization is any in-patient hospital admission for medical reasons, including an overnight stay in a healthcare facility, regardless of duration. A pre-existing condition that did not worsen while on study which involved a hospitalization for an elective treatment, is not considered an adverse event. Protocol specified hospitalizations are exempt.

At the top of Page 2, provide your Site Number and the Subject ID Number in the designated section.

5. IP Administration including Lot # and Serial # when known / available.

Blinded or open-label – If applicable, indicate whether the investigational product is blinded or open-label
Initial Start Date – Enter date the product was first administered, regardless of dose.

Date of Dose Prior to or at the time of the Event – Enter date the product was last administered prior to, or at the time of, the onset of the event.

Dose, Route, and Frequency at or prior to the event – Enter the appropriate information for the dose, route and frequency at, or prior to, the onset of the event.

Action Taken with Product – Enter the status of the product administration.

6. Concomitant Medications

Indicate if there are any medications.

Medication Name, Start Date, Stop Date, Dose, Route, and Frequency – Enter information for any other medications the subject is taking. Include any study drugs not included in section 5 (Product Administration) such as chemotherapy, which may be considered co-suspect.

Co-suspect – Indicate if the medication is co-suspect in the event

Continuing – Indicate if the subject is still taking the medication

Event Treatment – Indicate if the medication was used to treat the event

7. Relevant Medical History

Enter medical history that is relevant to the reported event, not the event description. This may include pre-existing conditions that contributed to the event allergies and any relevant prior therapy, such as radiation. Include dates if available.

8. Relevant Laboratory Tests

Indicate if there are any relevant laboratory values.

For each test type, enter the test name, units, date the test was run and the results.

9. Other Relevant Tests

Indicate if there are any tests, including any diagnostics or procedures.

For each test type, enter the date, name, results and units (if applicable).

At the top of Page 3, provide your Site Number and the Subject ID Number in the designated section.

10. Case Description

Describe Event – Enter summary of the event. Provide narrative details of the events listed in section 3. Include any therapy administered, such as radiotherapy; (excluding medications, which will be captured in section 6). If necessary, provide additional pages to Amgen.

Complete the signature section at the bottom of page 3 and send the form to Amgen. If the reporter is not the investigator, designee must be identified on the Delegation of Authority form.

AMGEN® Study # 2021004 AMG 757 Tarlatamab	Clinical Trial Electronic Serious Adverse Event Contingency Report Form For Restricted Use						
Notify Amgen Immediately and no later than 24 Hours of awareness of the serious adverse event/ other safety finding/special situation							
Reason for reporting this event using the Serious Adverse Event Contingency Report Form: The Clinical Trial Database (e.g. Rave):  Is not available due to internet outage at my study site  Is not yet available for this study  Has been closed for this study  Other Safety Finding/Special Situation associated with a Serious Adverse Event							
If this is a follow-up to an event reported in the EDC system (eg, Rave), provide the serious adverse event term: _____ and start date: Day _____ Month _____ Year _____							
<<Amgen Safety Fax Number to be populated by the Study Manager/Protocol Author/designee prior to providing to sites: SELECT OR TYPE IN A FAX#>>							
If an email address or eFax is used, the Primary Study Team (e.g., Clinical Manager or Delegate) will need to ensure secure email exchange is established between the Provider/Study Sites Vendor/Supplier, Sites and Amgen.							

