9.4.1 Planned Analyses

9.4.1.1 Interim Analysis and Early Stopping Guidelines

A description of the interim analysis and primary analysis is listed in [Table 9-1](#). An average accrual rate of [REDACTED] subjects per month with a [REDACTED]-month ramp-up period is assumed. Depending on the actual enrollment rate, the number and timing of interim analyses could be different from what is projected here.

Table 9-1. Purpose and Timing of the Planned Analyses

Timepoint	Adaptive Decision and Analysis Scope	Number of subjects or events	Timing
IA █% OS)	Efficacy/Safety	Total of █ OS events from both tarlatamab and SOC arm (the study is █ months fully enrolled)	█ months
OS PA	Efficacy/Safety	Total of █ OS events from both tarlatamab and SOC arm	█ months

IA = interim analysis; ORR = objective response rate; OS = overall survival; PA = planned analysis; SOC = standard of care.

An independent (external to Amgen) DMC will review unblinded interim safety and efficacy data as per DMC charter. The safety interim assessment from this committee will be approximately every 6 months afterward. If any safety interim is within 2 months of the IA, they may be combined.

Additionally, Amgen Pharmacovigilance conducts ongoing safety monitoring of blinded data throughout the clinical study.

Interim Efficacy Rules:

The testing of OS at the interim and primary analyses is adjusted using the Lan-DeMets alpha spending function with an O'Brien-Fleming approach. [Table 9-2](#) shows the efficacy boundaries, which if crossed will enable claiming of OS efficacy. Data will be subject to ongoing checks for integrity, completeness, and accuracy in accordance with the Data Management Plan with the expectation that outstanding data issues are resolved ahead of the lock to the extent possible. The data supporting the interim analysis will be locked to prevent further changes.

Table 9-2. Stopping Boundaries of OS

Analysis	Information Fraction	Cumulative Events	Alpha spending	p-value (primary inference)	HR boundary
Interim					
Primary					

HR = hazard ratio; OS = overall survival.

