11.3 Appendix 3. Study Governance Considerations

Data Monitoring Committee (DMC)

An independent external review committee, the Data Monitoring Committee (DMC) will review unblinded interim safety and efficacy data, and provide recommendations related to continuing, modifying, or stopping the study.

The DMC will review all available safety and efficacy data periodically every 6 months.

An Independent Biostatistics Group (IBG) will provide the analyses to the DMC. The IBG and DMC will have access to subjects' individual treatment assignments. To minimize the potential introduction of bias to the conduct of the study, members of the DMC will not have any direct contact with study site personnel or subjects. The DMC will communicate major safety concerns and recommendations regarding study modification or termination based on the safety and efficacy parameters to Amgen in accordance with the DMC charter.

Records of all meetings will be maintained by the DMC for the duration of the study.

Records of all meetings will be transferred and stored in the trial master file at the conclusion of the study. Further details are provided in the DMC charter.

Data Access Plan (DAP) Team

The Data Access Plan (DAP) team will convene for decision-making when DMC's recommendation is to stop study early, either for futility or for success. Details will be included in a separate DAP charter document.

Regulatory and Ethical Considerations

This study will be conducted in accordance with the protocol and with:

- Consensus ethical principles derived from international guidelines including the Declaration of Helsinki and Council for International Organizations of Medical Sciences International Ethical Guidelines
- Applicable International Council for Harmonisation (ICH) Good Clinical Practice (GCP) Guidelines
- Applicable ICH laws and regulations

The protocol, protocol amendments, informed consent form (ICF), Investigator's Brochure, and other relevant documents (eg, subject recruitment advertisements) must be submitted to an Institutional Review Board (IRB)/Independent Ethics Committee (IEC) by the investigator and reviewed and approved by the IRB/IEC. A copy of the written

approval of the protocol and ICF must be received by Amgen before recruitment of subjects into the study and shipment of Amgen investigational product.

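### Do the 6-monthly DMC efficacy reviews and the futility wording in Appendix 3 conflict with the OS stopping rules in Section 9.4.1.1?

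*Protocol*

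**What the plan says.** Two parts of the protocol bear on this.

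**Appendix 3 (Section 11.3).** On the Data Monitoring Committee: "The DMC will review all available safety and efficacy data periodically every 6 months". An independent biostatistics group supplies the analyses, and the DMC charter holds further detail. On the DAP team: it meets when the DMC's "recommendation is to stop study early, either for futility or for success". That paragraph ends: "Details will be included in a separate DAP charter document".

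**Section 9.4.1.1.** An independent "DMC will review unblinded interim safety and efficacy data as per DMC charter". Then: "The safety interim assessment from this committee will be approximately every 6 months afterward". And: "If any safety interim is within 2 months of the IA, they may be combined". In Table 9-1 the column headed "Adaptive Decision and Analysis Scope" lists efficacy and safety for both the interim and the primary analysis. OS testing uses Lan-DeMets spending of the O'Brien-Fleming type, and Table 9-2 "shows the efficacy boundaries, which if crossed will enable claiming of OS efficacy". The headings of Table 9-2 cover information fraction, events, alpha spending, p-value and HR boundary; none is for futility. Section 9.4.1.2 adds that the interim serves as the primary OS analysis if its boundary is crossed.

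The SAP supplied is an integrated safety plan that excludes formal hypothesis testing (SAP Section 5.2), so it does not address OS monitoring.

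**The concern.** There are two apparent mismatches.

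- **Content of the 6-monthly review.** Appendix 3 says it covers all efficacy data. Section 9.4.1.1 calls it a safety interim and has a rule for merging it with the OS interim, which implies two different reviews. If comparative OS results reach the DMC every 6 months, a reader asks whether there are more efficacy looks than the spending plan allows for.
- **Futility.** Appendix 3 foresees a futility recommendation. The section that sets the early stopping guidelines shows no futility criterion and does not say whether such a rule would bind.

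At stake would be type I error, if success could be declared at an unplanned look, and power, if the trial could be stopped for futility on an unstated rule.

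**Working it through.** **Step 1: the texts side by side.**

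| Question | Appendix 3 | Section 9.4.1.1 | Do they conflict? |
|---|---|---|---|
| Does the DMC see unblinded efficacy data? | Yes | Yes, under the charter | No |
| What is the 6-monthly review called? | Review of safety and efficacy data | Safety interim | Label only; nothing limits the data to safety |
| When can OS success be claimed? | Not stated | When a Table 9-2 boundary is crossed | No |
| Is a futility recommendation possible? | Yes | Not mentioned and not excluded | Detail is missing |

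One ordinary reading satisfies both places: every 6 months the DMC judges safety with efficacy alongside, as benefit-risk, and the formal OS test is made at the interim and the primary analysis. The merging rule is about meeting logistics. It separates the periodic review from the formal test but does not define the data package.

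**Step 2: inputs for the numerical check.** The plan's alpha, power, events and information fraction are redacted, so there is no stated figure to reproduce. Assumed: one-sided alpha 0.025; interim at t = 0.60 to 0.80 of the OS events; power 80% or 90%.

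**Step 3: boundaries.** Spending function: α(t) = 2[1 − Φ(z₁₋α/₂ / √t)], with z₁₋α/₂ = 2.2414. At t = 0.70, 2.2414/√0.70 = 2.679, so α(0.70) = 0.0074 and the interim bound is z = 2.438. The final bound makes the total 0.025.

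| t | Interim z | Final z | Type I error |
|---|---|---|---|
| 0.60 | 2.669 | 1.981 | 0.0250 |
| 0.70 | 2.438 | 2.000 | 0.0250 |
| 0.75 | 2.340 | 2.012 | 0.0250 |
| 0.80 | 2.250 | 2.025 | 0.0250 |

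**Step 4: extra looks without a success claim.** I simulated 2 to 5 DMC reviews before the interim (1,000,000 paths per case), with success allowed only at the two boundaries above. Type I error was 0.0246 to 0.0253, which is 0.025 within simulation error. Inflation appears only if success may be declared at a periodic review: 0.029 to 0.050 when the interim bound is reused at each review, and 0.055 to 0.083 with an unadjusted one-sided p < 0.025. No passage allows either.

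**Step 5: a futility stop, for scale only.** The criteria below are mine; the documents give none. The stop is applied once, at the planned interim, with the efficacy bounds unchanged. Conditional power under the current trend is 1 − Φ[(c − z√t − (z/√t)(1 − t)) / √(1 − t)], where c is the final bound. Setting it to 10%, 20% and 30% at t = 0.70 gives z = 1.086, 1.288 and 1.433.

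| Criterion | Power loss at t = 0.70, 80% / 90% power (points) | Range over t = 0.60 to 0.80 and both powers |
|---|---|---|
| Observed HR > 1 | 0.01 / 0.00 | under 0.1 |
| Conditional power < 10% | 1.60 / 1.17 | 0.7 to 2.4 |
| Conditional power < 20% | 3.16 / 2.35 | 1.6 to 4.4 |
| Conditional power < 30% | 4.88 / 3.68 | 2.5 to 6.5 |

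Type I error is 0.020 to 0.025 throughout. A harsher invented rule, stopping whenever the observed HR exceeds 1 at any of 2 to 5 reviews before the interim, takes power from about 0.90 to between 0.75 and 0.87 and type I error to between 0.018 and 0.023. The spread shows that the answer is set by the rule one invents, not by the plan.

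**The case for a change.** The strongest case for a change is this. The statistics group that prepares the DMC's reports needs to know what goes into each 6-monthly package, and the two places describe that package differently. Futility is a named outcome that could end the trial, yet the protocol shows neither a criterion nor a statement that it would be non-binding. The table headings are legible, so redaction does not explain the gap. Two sentences in Appendix 3 would close both points.

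Part of this stands. The word futility has no visible definition, and a pointer to the document that holds one would be tidier. The rest is weaker.

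- Section 9.4.1.1 gives the statistics group no instruction at all, and no passage tells it to leave efficacy data out.
- The DAP sentence says when a team meets; it creates no analysis, boundary or extra look. A DMC can advise stopping for futility on its general remit, and a scope of efficacy and safety does not rule that out.
- The detail is expressly assigned to the DMC and DAP charters. The study SAP promised in Section 9.4 is not among the documents either, so the absence of a rule here is weak evidence that none exists.
- A sentence limiting success to Table 9-2 would repeat what Sections 9.4.1.1 and 9.4.1.2 already say.

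Section 9.4.1.1 also allows the number and timing of interims to differ from projection. That does not reopen the type I error question: re-spending alpha with the same function at every review also gave about 0.025 in the simulation.

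**Conclusion.** The concern does not call for a change. The first point is a difference of label, since both places give the DMC unblinded efficacy data. The second is a detail left to charters, which a DMC and its statistics group would ordinarily settle there.

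Followed as written, the plan keeps type I error at its nominal level (0.025 one-sided, assumed) and loses no power. This rests on success being claimed only at a Table 9-2 boundary, which the protocol states. The power losses in the working, from under 0.1 to 6.5 points for one futility look, measure hypothetical rules and not a defect of this plan.

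A pointer from futility to the relevant charter would be a harmless editorial touch if the protocol were being amended for other reasons. It does not justify an amendment of its own across about 240 sites. If the charters proved to set a binding futility rule, or to allow a success claim at a periodic review, the question would need to be looked at again.
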